10.8 REPORTING FORMAT OR FREQUENCY

FDA may require a sponsor to submit IND safety reports in a format or at a frequency different than that required under this paragraph. The sponsor may also propose and adopt a different reporting format or frequency if the change is agreed to in advance by the director of the FDA review division that has responsibility for review of the IND.

10.9 INVESTIGATIONS OF MARKETED DRUGS

A sponsor of a clinical study of a drug marketed or approved in the United States that is conducted under an IND is required to submit IND safety reports for suspected adverse reactions that are observed in the clinical study, at domestic or foreign study sites. The sponsor must also submit safety information from the clinical study as prescribed by the post marketing safety reporting requirements.

10.10 REPORTING STUDY ENDPOINTS

Study endpoints (e.g., mortality or major morbidity) must be reported to FDA by the sponsor as described in the protocol and ordinarily would not be reported under Section 10.11 third bullet of this section. However, if a serious and unexpected adverse event occurs for which there is evidence suggesting a causal relationship between the drug and the event (e.g., death from anaphylaxis), the event must be reported under *Serious and unexpected suspected adverse reaction* as a serious and unexpected suspected adverse reaction even if it is a component of the study endpoint (e.g., all-cause mortality).

10.11 FOLLOW-UP

- The sponsor must promptly investigate all safety information it receives.
- Relevant follow-up information to an IND safety report must be submitted as soon as the information is available and must be identified as such, i.e., "Follow-up IND Safety Report."
- If the results of a sponsor's investigation show that an adverse event not initially determined to be reportable under section IND safety reports of this section is so reportable, the sponsor must report such suspected adverse reaction in an IND safety report as soon as possible, but in no case later than 15 calendar days after the determination is made.

10.12 DISCLAIMER

A safety report or other information submitted by a sponsor under this part (and any release by FDA of that report or information) does not necessarily reflect a conclusion by the sponsor or FDA that the report or information constitutes an admission that the drug caused or contributed to an adverse event. A sponsor need not admit, and may deny, that the report or information submitted by the sponsor constitutes an admission that the drug caused or contributed to an adverse event.

The Sponsor-Investigator must promptly review all information relevant to the safety of the drug obtained or otherwise received from foreign or domestic sources, including information derived from any clinical or epidemiological investigations, animal or in vitro studies, reports in the scientific literature, and unpublished scientific papers, as well as reports from foreign regulatory authorities and reports of foreign commercial marketing experience for drugs that are not marketed in the United States. The study sponsor must notify all participating investigators of potential serious risks, from clinical trials or any other source, as soon as possible.

10.13 ADDITIONAL SITE AND SPONSOR-INVESTIGATOR RESPONSIBILITIES TO BRISTOL-MYERS SQUIBB (BMS)

The Sponsor-investigator will reconcile the clinical database SAE cases (case level only) transmitted to BMS Global Pharmacovigilance ([contact]) (BMS GPV&E). Frequency of reconciliation should be every 3 months and prior to the database lock or final data summary. BMS GPV&E will email, upon request from the Investigator, the GPV&E reconciliation report. Requests for reconciliation should be sent to [contact]. The data elements listed on the GPV&E reconciliation report will be used for case identification purposes. If the Investigator determines a case was not transmitted to BMS GPV&E, the case should be sent immediately to BMS. In accordance with local regulations, BMS will notify investigators of all reported SAEs that are suspected (related to the investigational product) and unexpected (ie, not previously

described in the IB). An event meeting these criteria is termed a Suspected, Unexpected Serious Adverse Reaction (SUSAR). Investigator notification of these events will be in the form of a SUSAR Report

UPMC Hillman Cancer Center acknowledges and agrees that the Study Drug Relatlimab is a BMS early asset and the safety and efficacy of the Study drug is not as well-known as a marketed drug or drug in late-development. Notwithstanding that BMS is not the regulatory sponsor of the Study, in order to protect the safety and well-being of Study subjects, UPMC Hillman agrees to collaborate with BMS on safety issues arising from the Study Drug

UPMC Hillman Cancer Center shall disclose de-identified, patient level Study Data to BMS upon request, and in the format reasonably requested by BMS under this Agreement. BMS shall have unlimited rights to access, use, or disclose this Study Data for internal research and development purposes or to support an application to the FDA and other regulatory authorities without further obligation to UPMC Hillman Cancer Center or the sponsor-investigator.

11.0 DATA SAFETY MONITORING PLAN

Investigator/Sub-investigators, regulatory, CRS management, clinical research coordinators, clinical research associates, data managers, and clinic staff meet regularly in disease center Data Safety Monitoring Boards (DSMB) to review and discuss study data to include, but not limited to, the following:

- serious adverse events
- subject safety issues
- recruitment issues
- accrual
- protocol deviations
- unanticipated problems
- breaches of confidentiality

Minutes from the disease center DSMB meetings are available to those who are unable to attend in person.

All toxicities encountered during the study will be evaluated on an ongoing basis according to the NCI Common Toxicity Criteria Version 5.0. All study treatment associated adverse events that are serious, at least possibly related and unexpected will be reported to the IRB and FDA. Any modifications necessary to ensure subject safety and decisions to continue or close the trial to accrual are also discussed during these meetings. If any literature becomes available which changes the risk/benefit ratio or suggests that conducting the trial is no longer ethical, the IRB will be notified in the form of an Unanticipated Problem submission and the study may be terminated.

All study data reviewed and discussed during these meetings will be kept confidential. Any breach in subject confidentiality will be reported to the IRB in the form of an Unanticipated Problem submission. The summaries of these meetings are forwarded to the UPMC Hillman Cancer Center DSMC which also meets monthly following a designated format.

For all research protocols, there will be a commitment to comply with the IRB's policies for reporting unanticipated problems involving risk to subjects or others (including adverse events). DSMC progress reports, to include a summary of all serious adverse events and modifications, and approval will be submitted to the IRB at the time of renewal.

Protocols with subjects in long-term (survival) follow-up or protocols in data analysis only, will be reviewed bi-annually.

Both the UPMC Hillman Cancer Center DSMC as well as the individual disease center DSMB have the authority to suspend accrual or further investigate treatment on any trial based on information discussed at these

meetings.. If the DSMB recommends any study changes related to safety, the sponsor-investigator will also notify BMS and FDA.

All records related to this research study will be stored in a locked environment. Only the researchers affiliated with the research study and their staff will have access to the research records.

12.0 MANAGEMENT OF ADVERSE EVENTS

12.1 IMMUNE RELATED ADVERSE EVENTS

For the purposes of this study, an immune-related adverse reaction is defined as an adverse reaction of unknown etiology associated with drug exposure and consistent with an immune phenomenon. Efforts should be made to rule out neoplastic, infectious, metabolic, toxin or other etiologic causes prior to labeling an event an irAEs. Serologic, immunologic, and histologic (biopsy) data should be used to support the diagnosis of an immune-related toxicity. Suspected immune-related adverse reactions must be documented on an AE or SAE form.

Patients should be informed of and carefully monitored for evidence of clinically significant systemic immune-mediated adverse reactions (e.g., systemic lupus erythematosus-like diseases) or organ-specific immune-mediated adverse reaction (e.g., rash, colitis, uveitis, hepatitis or thyroid disease). If an immune-mediated adverse reaction is noted, appropriate work-up (including biopsy if possible) should be performed, and steroid therapy may be considered if clinically necessary.

Recommended guidelines for specific immune-mediated adverse reactions are included in Appendix II. These recommendations should be utilized as clinically appropriate for the treatment of individual patients. Please contact the PI for any questions

12.2 DOSE DELAY CRITERIA:

Toxicity from Ipilimumab plus Nivolumab and Relatlimab plus Nivolumab will be graded by CTCAE v5.0. No dose reductions will occur for drug related adverse events but rather drug therapy will be held and next cycle delayed.

Subjects who experience the following must have all study drugs held:

Select drug-related AEs and drug-related laboratory abnormalities:

- \geq Grade 2 pneumonitis
- \geq Grade 2 elevation of liver tests (AST or ALT and/or total bilirubin)
- \geq Grade 2 increased creatinine
- \geq Grade 2 diarrhea or colitis
- \geq Grade 2 neurological AE
- \geq Grade 3 skin AE
- Myocarditis (any grade)
- All troponin elevations require a dose delay to allow for prompt cardiac evaluation. Following this evaluation, determination of further treatment will be based on the discretion of the PI.
- Grade 4 amylase and/or lipase abnormalities regardless of symptoms or clinical manifestations.
- Any adverse event, laboratory abnormality, or intercurrent illness which, in the judgment of the investigator, warrants delaying the dose of study medication.

Subjects that have drug-related toxicities that meet the criteria for dose delay, should have both drugs delayed until retreatment criteria are met. When retreatment criteria are met, subsequent dosing visits will follow every 2 weeks (or 4 weeks as applicable) after the delayed dose.

12.3 ADVERSE EVENT TREATMENT DISCONTINUATION CRITERIA

1. Any Grade ≥ 2 drug-related uveitis, eye pain or blurred vision that does not respond to topical therapy and does not improve to Grade 1 severity within the re-treatment period OR requires systemic treatment
2. Any Grade ≥ 3 non-skin, drug-related AE lasting > 7 days, or recurs with the following exceptions for laboratory abnormalities, diarrhea, colitis, neurologic toxicity, drug-related uveitis, pneumonitis, bronchospasm, hypersensitivity reactions, infusion reactions, and endocrinopathies:
 - a. Grade ≥ 3 drug-related myocarditis, diarrhea, colitis, neurologic toxicity, uveitis, pneumonitis, bronchospasm, hypersensitivity reaction, or infusion reaction of any duration requires discontinuation:-- Grade ≥ 3 drug-related endocrinopathies, adequately controlled with only physiologic hormone replacement do not require discontinuation. Adrenal insufficiency requires discontinuation regardless of control with hormone replacement.
 - b. Grade > 3 drug-related laboratory abnormalities do not require treatment discontinuation except:
 - i. Grade > 3 drug-related thrombocytopenia > 7 days or associated with bleeding requires discontinuation
 - c. Any drug-related liver function test (LFT) abnormality that meets the following criteria require discontinuation:
 - i. Grade > 3 drug-related AST, ALT or Total Bilirubin requires discontinuation*
 - ii. Concurrent AST or ALT $> 3 \times$ ULN and total bilirubin $> 2 \times$ ULN
- * In most cases of Grade 3 AST or ALT elevation, study treatment will be permanently discontinued. If the investigator determines a possible favorable benefit/risk ratio that warrants continuation of study treatment, a discussion between the investigator and the Sponsor
3. Any Grade 4 drug-related adverse event or laboratory abnormality (including but not limited to creatinine, AST, ALT, or Total Bilirubin), except for the following events which do not require discontinuation:
 - Grade 4 neutropenia ≤ 7 days
 - Grade 4 lymphopenia or leukopenia or asymptomatic amylase or lipase
 - Isolated Grade 4 electrolyte imbalances/abnormalities that are not associated with clinical sequelae and are corrected with supplementation/appropriate management within 72 hours of their onset
 - Grade 4 drug-related endocrinopathy adverse events, such as, hyper- or hypothyroidism, or glucose intolerance, which resolve or are adequately controlled with physiologic hormone replacement (corticosteroids, thyroid hormones) or glucose-controlling agents, respectively, may not require discontinuation after discussion with and approval from the Sponsor.
4. Any event that leads to delay in dosing lasting > 6 weeks from the previous dose requires discontinuation, with the following exceptions:
 - Dosing delays to allow for prolonged steroid tapers to manage drug-related adverse events are allowed. A drug related adverse event where steroids are not indicated but the management of the adverse event causes a dose delay lasting > 6 weeks may be allowed if approved by the Sponsor.
 - Dosing delays lasting > 6 weeks from the previous dose that occur for non-drug-related reasons may be allowed if approved by the Sponsor.
5. Any adverse event, laboratory abnormality, or intercurrent illness which, in the judgment of the Investigator, presents a substantial clinical risk to the participant with continued study drug combination dosing.
6. Prior to re-initiating treatment in a participant with a dosing delay lasting > 6 weeks, the sponsor must be consulted. Tumor assessments should continue as per protocol even if dosing is delayed. Periodic study

visits to assess safety and laboratory studies should also continue if clinically indicated during such dosing delays.

7. Subjects who meet criteria for permanent discontinuation should receive no further study therapy. The following exceptions apply:

- If the toxicity resolves to < Grade 1 or baseline > 6 weeks after last dose, but the subject does not otherwise meet the criteria for permanent discontinuation and the Investigator believes that the subject is deriving clinical benefit, then the subject may be eligible to resume the study drug(s) following the approval of the sponsor.
- Subjects with a grade 4 drug-related amylase and/or lipase increase that is not associated with symptoms or clinical manifestations of pancreatitis can be restarted on therapy once the levels have recovered to grade 3 or less, and after consultation with the sponsor.
- Subjects with baseline Grade 1 AST, ALT, or total bilirubin who require dose delays for reasons other than a drug-related hepatic event may resume treatment in the presence of Grade 2 AST, ALT, or total bilirubin.
- Subjects who require dose delays for drug-related elevations in AST, ALT, or total bilirubin may resume treatment when these values have returned to their baseline CTCAE Grade or normal, provided the criteria for permanent discontinuation are not met.
- Subjects may resume treatment in the presence of Grade 2 fatigue.
- Drug-related endocrinopathies adequately controlled with only physiologic hormone replacement may resume treatment.

12.4 INFUSION REACTIONS:

Treatment recommendations are provided below and may be modified based on local treatment standards and guidelines, as appropriate:

For Grade 1 symptoms (Mild reaction; infusion interruption not indicated; intervention not indicated):

- Remain at bedside and monitor subject until recovery from symptoms. The following prophylactic premedications are recommended for future infusions: diphenhydramine 50 mg (or equivalent) and/or acetaminophen/paracetamol 325 to 1000 mg at least 30 minutes before additional study drug administrations.

For Grade 2 symptoms (Moderate reaction requires therapy or infusion interruption but responds promptly to symptomatic treatment [e.g., antihistamines, non-steroidal anti- inflammatory drugs, narcotics, corticosteroids, bronchodilators, IV fluids]; prophylactic medications indicated for ≤ 24 hours).

- Stop the infusion, begin an IV infusion of normal saline, and treat the subject with diphenhydramine 50 mg IV (or equivalent) and/or acetaminophen/paracetamol 325 to 1000 mg; remain at bedside and monitor subject until resolution of symptoms. Corticosteroid and/or bronchodilator therapy may also be administered as appropriate. If the infusion is interrupted, then restart the infusion at 50% of the original infusion rate when symptoms resolve; if no further complications ensue after 30 minutes, the rate may be increased to 100% of the original infusion rate. Monitor subject closely. If symptoms recur, then no further study drug will be administered at that visit.
- For future infusions, the following prophylactic premedications are recommended:
- Diphenhydramine 50 mg (or equivalent) and/or acetaminophen/paracetamol 325 to 1000 mg should be administered at least 30 minutes before study drug infusions.
- If necessary, corticosteroids (up to 25 mg of SoluCortef or equivalent) may be used.

For Grade 3 or 4 symptoms (Severe reaction, Grade 3: prolonged [i.e., not rapidly responsive to symptomatic medication and/or brief interruption of infusion]; recurrence of symptoms following initial improvement;

hospitalization indicated for other clinical sequelae [e.g., renal impairment, pulmonary infiltrates]. Life-threatening, Grade 4: pressor or ventilatory support indicated).

- Immediately discontinue infusion of study drug. Begin an IV infusion of normal saline and treat the subject as follows: Recommend bronchodilators, epinephrine 0.2 to 1 mg of a 1:1000 solution for subcutaneous (SC) administration or 0.1 to 0.25 mg of a 1:10,000 solution injected slowly for IV administration, and/or diphenhydramine 50 mg IV with methylprednisolone 100 mg IV (or equivalent), as needed. Subject should be monitored until the Investigator is comfortable that the symptoms will not recur.
- All study drug(s) will be permanently discontinued. Investigators should follow their institutional guidelines for the treatment of anaphylaxis. Remain at bedside and monitor subject until recovery of the symptoms.

In case of late-occurring hypersensitivity symptoms (e.g., appearance of a localized or generalized pruritus within 1 week after treatment), symptomatic treatment may be given (e.g., oral antihistamine or corticosteroids).

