12.5 CRITERIA TO RESUME TREATMENT

Subjects may resume treatment with combination therapy when the drug-related AE(s) resolve(s) to Grade \leq 1 or baseline and if applicable the patient is no longer on systemic steroids, with the following exceptions:

- Subjects may resume treatment in the presence of Grade 2 fatigue.
- Subjects who have not experienced a Grade 3 drug-related skin AE may resume treatment in the presence of Grade 2 skin toxicity.
- For participants with Grade 2 AST, ALT and/or Total Bilirubin Abnormalities, dosing may resume when laboratory values return to baseline and management with corticosteroids, if needed, is complete.
- Drug-related pulmonary toxicity, diarrhea, or colitis must have resolved to baseline before treatment is resumed. Subjects with persistent Grade 1 pneumonitis after completion of a steroid taper over at least 1 month may be eligible for retreatment if discussed with and approved by the Sponsor.

Participants with drug-related endocrinopathies adequately controlled with only physiologic hormone replacement may resume treatment after consultation with the Sponsor.

Adrenal insufficiency requires discontinuation regardless of control with hormone replacement.

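### Sections 12.3 and 12.5 set incompatible recovery levels for restarting after an asymptomatic Grade 4 amylase or lipase rise

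*Combined protocol and SAP*

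**What the plan says.** Section 12.2 names, among the findings for which all study drugs must be held, "Grade 4 amylase and/or lipase abnormalities regardless of symptoms or clinical manifestations". It adds that subjects who meet a delay criterion "should have both drugs delayed until retreatment criteria are met", with no reference to where those criteria are set out.

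Section 12.3 item 3 exempts some events from discontinuation at Grade 4, among them "Grade 4 lymphopenia or leukopenia or asymptomatic amylase or lipase". Item 7 of the same section is introduced as a list of exceptions for subjects who do meet the criteria for permanent discontinuation. One of its bullets says that subjects with a Grade 4 drug-related rise, but no symptoms or signs of pancreatitis, "can be restarted on therapy once the levels have recovered to grade 3 or less, and after consultation with the sponsor".

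Section 12.5 carries the heading for resuming treatment. It opens with "Subjects may resume treatment with combination therapy when the drug-related AE(s) resolve(s) to Grade" 1 or less, or baseline, and off systemic steroids where that applies. Its exceptions deal with fatigue, skin toxicity, liver tests, pulmonary toxicity with diarrhoea and colitis, and, after the bullets, endocrinopathy.

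Endocrinopathy and liver tests appear in both sections. In 12.3 item 7: "Drug-related endocrinopathies adequately controlled with only physiologic hormone replacement may resume treatment". In 12.5, participants with these conditions "adequately controlled with only physiologic hormone replacement may resume treatment after consultation with the Sponsor". For drug-related liver test elevations, item 7 asks for return to the baseline grade or to normal. For Grade 2 abnormalities, 12.5 asks for return to baseline and for any corticosteroid course to be finished.

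**The concern.** The hold in 12.2 ends when retreatment criteria are met, so those criteria decide whether a patient is dosed again. If two sections supply them at different grades, the same patient on the same day may be eligible for re-dosing and required to stay on hold.

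The first consequence is for the patient: exposure depends on which section the investigator reads, and either action can be called a deviation from the other section. The second is for monitoring. The toxicity pausing rule in 15.3.2 counts adverse events that warrant discontinuation under 12.3, and item 4 of that section makes a delay of more than 6 weeks from the previous dose a ground for discontinuation. The choice of restart text can therefore feed into the toxicity count.

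**Working it through.** No figure in the plan needs reproducing. The check is a comparison of texts plus one subtraction.

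**Does 12.5 reach a laboratory finding?** Yes. Section 9.6 classes a test finding as an adverse event if it leads to a change in study dosing, and a hold is such a change.

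**Restart rule for an asymptomatic Grade 4 amylase or lipase rise:**
- 12.3 item 7: Grade 3 or less, after sponsor consultation.
- 12.5: Grade 1 or less, or baseline; amylase and lipase are not among the exceptions.

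The two rules agree once the value is at Grade 1 or less, or back at baseline. They disagree for a patient who stays at Grade 2 or 3 from a lower baseline.

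**Does the framing of item 7 settle it?** No. Item 7 addresses subjects who meet permanent discontinuation criteria. Item 3 says that this event, without symptoms, is not such a criterion. Read literally, the Grade 3 route may not reach the patient it describes, which leaves 12.5 in force. Read for its evident purpose, it applies and 12.5 is overridden. The text supports either reading.

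**Time to the limit.** Weeks after the missed dose was due = 6 − dosing interval in weeks.
- Relatlimab plus nivolumab every 4 weeks, and nivolumab 480 mg from C6: 6 − 4 = 2 weeks.
- Nivolumab every 2 weeks (C1 to C5 with ipilimumab): 6 − 2 = 4 weeks.

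**Illustration.** A patient on relatlimab plus nivolumab has an asymptomatic Grade 4 lipase at C2D1, falling to Grade 2 after one week and staying there, with a normal baseline. Under item 7 the patient may restart after that week, following consultation. Under 12.5 the hold goes on; 2 weeks after the C2D1 due date the 6-week limit is reached, and any further delay means discontinuation by default. Item 4 lets the sponsor approve a longer delay where steroids are not indicated. That approval lengthens the hold; it does not say at what grade treatment may restart.

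**Effect on the count.** The same course contributes 0 or 1 event to Table 9. That changes a look only if the count otherwise stands one short: 2 against 3 of 10, 4 against 5 of 20, or 6 against 7 of 30.

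**Frequency.** Section 2.5.5 gives drug-related lipase increase of any grade as 6.5% of subjects on relatlimab plus nivolumab in Study CA224020. Section 8.5 puts raised lipase and raised amylase, each without grade, in the 5 to 10% band for nivolumab plus ipilimumab. Neither is a Grade 4 rate. The chemistry panels itemised in the notes to 7.1, 7.2 and 7.3 include neither amylase nor lipase.

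**The case against.** The best defence is that a bullet written for this exact event should be read as qualifying the general rule in 12.5. It also requires sponsor consultation, so the sponsor-investigator would settle each case. That is a reasonable way to run the trial, but the protocol does not state it. Section 12.5 keeps its own list of exceptions and repeats the fatigue exception from item 7 while leaving amylase and lipase out, so its list can fairly be taken as complete.

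A second defence is rarity, and much of it stands. The event must be Grade 4 and free of symptoms, and must then stall at Grade 2 or 3. With no scheduled amylase or lipase, a symptom-free rise would be found only by an unscheduled test, and a test ordered for symptoms of pancreatitis would fall outside the item 7 bullet.

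Third, the 6-week limit is not automatic: item 4 provides for sponsor approval of longer delays. Nor does Table 9 stop the trial; it pauses accrual, with possible amendment. Both points stand, and both limit the consequence without removing the conflict.

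Finally, the endocrinopathy and liver texts can each be satisfied together. They differ in an added condition (consultation, completed corticosteroids), not clearly in the recovery level. That is correct, and they are lesser mismatches.

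**Conclusion.** The conflict is real and confined to one event: for an asymptomatic Grade 4 amylase or lipase rise, the protocol gives two restart levels and no order of precedence. It affects a patient settling at Grade 2 or 3 from a lower baseline, and at most one event per such patient in the toxicity count. Counting a time-out there rests on reading item 4 discontinuations as events under 15.3.2, which is the plain sense of its reference to 12.3. The analysis of objective response is not affected.

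Four stronger readings may tempt a reader and are not supported:
- **About one relatlimab patient would be affected.** If half of the 40 patients received relatlimab, 0.065 × 20 = 1.3, but 6.5% is an any-grade rate and no Grade 4 rate is given.
- **The hold inevitably ends in discontinuation.** The sponsor may approve a longer delay.
- **Different sites would act differently.** Section 6.1 names a single centre; the risk is inconsistency between investigators or between occasions.
- **Several recovery levels conflict.** Only amylase and lipase clearly do.

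This should be corrected because it is an operative safety rule and the correction is nearly free, not because many patients are likely to be affected.

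**What to change.** Reconcile the passages so that 12.5 is the only source of restart criteria, and have 12.2 cite it by number where it refers to retreatment criteria. In 12.5, give amylase and lipase one recovery level and one statement on whether sponsor consultation is required. Settle there, in a single wording each, whether consultation is needed after controlled endocrinopathy and whether corticosteroids must be complete for liver tests. Remove from 12.3 item 7 the duplicate bullets that describe patients who were only delayed, leaving true exceptions to permanent discontinuation. The sponsor chooses the levels; none is proposed here.

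The cost is one editorial amendment, with no added visits, tests or patients.
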